10.3.2. Definition of an SAE

An SAE is defined as any untoward medical occurrence that, at any dose, meets one or more of the criteria listed below:

a. Results in death

b. Is life-threatening
 
The term “life-threatening” in the definition of “serious” refers to an event in which the participant was at risk of death at the time of the event. It does not refer to an event that hypothetically might have caused death if it were more severe.

c. Requires inpatient hospitalization or prolongation of existing hospitalization
 
In general, hospitalization signifies that the participant has been admitted (usually involving at least an overnight stay) at the hospital or emergency ward for observation and/or treatment that would not have been appropriate in the physician’s office or outpatient setting. Complications that occur during hospitalization are AEs. If a complication prolongs hospitalization or fulfills any other serious criteria, the event is serious. When in doubt as to whether “hospitalization” occurred or was necessary, the AE should be considered serious.
 
Hospitalization for elective treatment of a preexisting condition that did not worsen from baseline is not considered an AE.

090177e19fcc12ed\Approved\Approved On: 30-Jan-2024 19:45 (GMT)

d. Results in persistent or significant disability/incapacity

- The term disability means a substantial disruption of a person’s ability to conduct normal life functions.
- This definition is not intended to include experiences of relatively minor medical significance, such as uncomplicated headache, nausea, vomiting, diarrhea, influenza, and accidental trauma (eg, sprained ankle), that may interfere with or prevent everyday life functions but do not constitute a substantial disruption.

e. Is a congenital anomaly/birth defect

f. Is a suspected transmission via a Kanyos Bio, Inc. product of an infectious agent, pathogenic or nonpathogenic

The event may be suspected from clinical symptoms or laboratory findings indicating an infection in a participant exposed to a Kanyos Bio, Inc. product. The terms “suspected transmission” and “transmission” are considered synonymous. These cases are considered unexpected and handled as serious expedited cases by pharmacovigilance personnel. Such cases are also considered for reporting as product defects, if appropriate.

g. Other situations:

- Medical or scientific judgment should be exercised by the investigator in deciding whether SAE reporting is appropriate in other situations, such as significant medical events that may jeopardize the participant or may require medical or surgical intervention to prevent one of the other outcomes listed in the above definition. These events should usually be considered serious.
- Examples of such events include invasive or malignant cancers, intensive treatment in an emergency room or at home for allergic bronchospasm, blood dyscrasias or convulsions that do not result in hospitalization, or development of drug dependency or drug abuse.

10.3.3. Recording/Reporting and Follow-Up of AEs and/or SAEs During the Active Collection Period

AE and SAE Recording/Reporting		

The table below summarizes the requirements for recording AEs on the CRF and for reporting SAEs on the CT SAE Report Form to Pfizer Safety throughout the active collection period. These requirements are delineated for 3 types of events: (1) SAEs; (2) nonserious AEs; and (3) exposure to the study intervention under study during pregnancy or breastfeeding, and occupational exposure.
 
It should be noted that the CT SAE Report Form for reporting of SAE information is not the same as the AE page of the CRF. When the same data are collected, the forms must be completed in a consistent manner. AEs should be recorded using concise medical terminology and the same AE term should be used on both the CRF and the CT SAE Report Form for reporting of SAE information.
		
Safety Event	Recorded on the CRF	Reported on the CT SAE Report Form to Pfizer Safety Within 24 Hours of Awareness
SAE	All	All
Nonserious AE	All	None
Exposure to the study intervention under study during pregnancy or breastfeeding	All AEs or SAEs associated with EDP or EDB Note: Instances of EDP or EDB not associated with an AE or SAE are not captured in the CRF	All instances of EDP are reported (whether or not there is an associated SAE)* All instances of EDB are reported (whether or not there is an associated SAE)**
Environmental or occupational exposure to the product under study to a nonparticipant (not involving EDP or EDB)	None. Exposure to a study nonparticipant is not collected on the CRF	The exposure (whether or not there is an associated AE or SAE) must be reported***

* EDP (with or without an associated SAE): is reported to Pfizer Safety using the CT SAE Report Form and EDP Supplemental Form; if the EDP is associated with an SAE, then the SAE is reported to Pfizer Safety using the CT SAE Report Form.
 
** EDB is reported to Pfizer Safety using the CT SAE Report Form, which would also include details of any SAE that might be associated with the EDB.
 
*** Environmental or occupational exposure: AEs or SAEs associated with occupational exposure are reported to Pfizer Safety using the CT SAE Report Form.
		

090177e19fcc12ed\Approved\Approved On: 30-Jan-2024 19:45 (GMT)

- When an AE or SAE occurs, it is the responsibility of the investigator to review all documentation (eg, hospital progress notes, laboratory reports, and diagnostic reports) related to the event.
- The investigator will then record all relevant AE or SAE information in the CRF.
- It is **not** acceptable for the investigator to send photocopies of the participant’s medical records to Pfizer Safety in lieu of completion of the CT SAE Report Form/AE or SAE CRF page.
- There may be instances when copies of medical records for certain cases are requested by the sponsor/Pfizer Safety. In this case, all participant identifiers, with the exception of the participant number, will be redacted on the copies of the medical records before submission to Pfizer Safety.
- The investigator will attempt to establish a diagnosis of the event based on signs, symptoms, and/or other clinical information. Whenever possible, the diagnosis (not the individual signs/symptoms) will be documented as the AE or SAE.

Assessment of Intensity

The investigator will make an assessment of intensity for each AE and SAE reported during the study and assign it to 1 of the categories listed below (as defined by the NCI CTCAE system).

GRADE	Clinical Description of Intensity
1	MILD AE
2	MODERATE AE
3	SEVERE AE
4	LIFE-THREATENING; urgent intervention indicated
5	DEATH RELATED TO AE

Further details regarding the CTCAE are presented in [Appendix 10](#).

An event is defined as “serious” when it meets at least 1 of the predefined outcomes as described in the definition of an SAE, NOT when it is rated as severe.

Assessment of Causality

- The investigator is obligated to assess the relationship between study intervention and each occurrence of each AE or SAE. The investigator will use clinical judgment to determine the relationship.
- A “reasonable possibility” of a relationship conveys that there are facts, evidence, and/or arguments to suggest a causal relationship, rather than a relationship cannot be ruled out.
- Alternative causes, such as underlying disease(s), concomitant therapy, and other risk factors, as well as the temporal relationship of the event to study intervention administration, will be considered and investigated.
- The investigator will also consult the IB and/or product information, for marketed products, in their assessment.
- For each AE or SAE, the investigator **must** document in the medical notes that they have reviewed the AE or SAE and have provided an assessment of causality.
- There may be situations in which an SAE has occurred and the investigator has minimal information to include in the initial report to Pfizer Safety . However, **it is very important that the investigator always make an assessment of causality for every event before the initial transmission of the SAE data to Pfizer Safety.**
- The investigator may change their opinion of causality in light of follow-up information and send an SAE follow-up report with the updated causality assessment.
- The causality assessment is one of the criteria used when determining regulatory reporting requirements.
- If the investigator does not know whether or not the study intervention caused the event, then the event will be handled as “related to study intervention” for reporting purposes, as defined by Pfizer Safety. In addition, if the investigator determines that an SAE is associated with study procedures, the investigator must record this causal relationship in the source documents and CRF, and report such an assessment in the dedicated section of the CT SAE Report Form and in accordance with the SAE reporting requirements.

Follow-Up of AEs and SAEs

- The investigator is obligated to perform or arrange for the conduct of supplemental measurements and/or evaluations, as medically indicated or as requested by the sponsor/Pfizer Safety, to elucidate the nature and/or causality of the AE or SAE as fully as possible. This may include additional laboratory tests or investigations, histopathological examinations, or consultation with other healthcare providers.
- If a participant dies during participation in the study or during a recognized follow-up period, the investigator will provide Pfizer Safety with a copy of any postmortem findings, including histopathology.
- New or updated information will be recorded in the originally submitted documents.
- The investigator will submit any updated SAE data to Pfizer Safety within 24 hours of receipt of the information.

10.3.4. Reporting of SAEs

SAE Reporting to Sponsor Safety via an Electronic DCT

- The primary mechanism for reporting an SAE to Pfizer Safety will be the electronic DCT.
- If the electronic system is unavailable, then the site will use the paper SAE DCT (see next section) to report the event within 24 hours.
- The site will enter the SAE data into the electronic DCT (eg, eSAE or PSSA) or paper form (as applicable) as soon as the data become available.
- After the study is completed at a given site, the electronic DCT will be taken off-line to prevent the entry of new data or changes to existing data.
- If a site receives a report of a new SAE from a study participant or receives updated data on a previously reported SAE after the electronic DCT has been taken off-line, then the site can report this information on a paper SAE form (see next section) or to Pfizer Safety by telephone.

SAE Reporting to Sponsor Safety via the CT SAE Report Form

- Facsimile transmission of the CT SAE Report Form is the preferred method to transmit this information to Pfizer Safety.
- In circumstances when the facsimile is not working, an alternative method should be used, eg, secured (Transport Layer Security) or password-protected email. If none of these methods can be used, notification by telephone is acceptable with a copy of the CT SAE Report Form sent by overnight mail or courier service.
- Initial notification via telephone does not replace the need for the investigator to complete and sign the CT SAE Report Form pages within the designated reporting time frames.

10.4. Appendix 4: Contraceptive and Barrier Guidance

10.4.1. Male Participant Reproductive Inclusion Criteria (Parts A and B)

Male participants are eligible to participate if they agree to the following requirements during the intervention period and for at least 21 days after the last dose of study intervention, which corresponds to the time needed to eliminate reproductive safety risk of the study intervention(s):

- Refrain from donating sperm.

PLUS either:

- Be abstinent from heterosexual or homosexual intercourse as their preferred and usual lifestyle (abstinent on a long-term and persistent basis) and agree to remain abstinent.

OR

- Must agree to use a male condom when engaging in any activity that allows for passage of ejaculate to another person.
- The male participant should be advised of the benefit for a WOCBP partner using a highly effective method of contraception with a failure rate of <1% per year, as described in [Section 10.4.4](#).

10.4.2. Female Participant Reproductive Inclusion Criteria (Parts A and B)

The criteria below are part of Inclusion Criterion 1 (Age and Sex; [Section 5.1](#)) and specify the reproductive requirements for including female participants. Refer to [Section 10.4.4](#) for a complete list of contraceptive methods permitted in the study.

- A female participant is eligible to participate if she (a) is not pregnant or breastfeeding; and (b) agrees not to donate eggs (ova, oocytes) for the purpose of reproduction for 21 days after the last dose of study intervention; and (c) at least 1 of the following conditions applies:

- Is not a WOCBP (see definition in [Section 10.4.3](#)).

OR

- Is a WOCBP and agrees to use a contraceptive method that is highly effective (failure rate of <1% per year) with low user dependency during the intervention period and agrees to use it for at least 21 days after the last dose of study intervention, which corresponds to the time needed to eliminate any reproductive safety risk of the study intervention(s). The investigator should evaluate the effectiveness of the contraceptive method in relationship to the first dose of study intervention.

OR

- Is a WOCBP and agrees to use a highly effective (failure rate of <1% per year) user-dependent method of contraception during the intervention period and for at least 21 days after the last dose of study intervention, which corresponds to the time needed to eliminate any reproductive safety risk of the study intervention(s). In addition to her use of the highly effective method above, she agrees to concurrently use an effective barrier method. The investigator should evaluate the effectiveness of the contraceptive method in relationship to the first dose of study intervention.

The investigator is responsible for review of medical history, menstrual history, and recent sexual activity to decrease the risk for inclusion of a woman with an early undetected pregnancy.

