4.2.1. Choice of Contraception/Barrier Requirements

KAN-101 has not been evaluated in EFD study. The effects of KAN-101 on conception, pregnancy, and lactation are unknown. Therefore, the use of a highly effective contraception and a barrier method is required for WOCBP, and all men who are not sterile (biologically or surgically) must commit to the use of 1 reliable method of birth control for at least 21 days after the last dose of study intervention (see [Appendix 4](#) for further information).

The observed $t_{1/2}$ of KAN-101 from the FIH study ranges between 3.74 to 36.8 minutes across 0.15 mg/kg to 1.2 mg/kg doses with no accumulation observed for repeat dosing. Pre-clinical toxicology and clinical information for KAN-101 are summarized in the IB.

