5.1. Inclusion Criteria

Participants are eligible to be included in the study only if all of the following criteria apply:

Age and Sex:

1. Participants aged 18 years to 70 inclusive (or the minimum age of consent in accordance with local regulations) at screening.
 - Refer to [Appendix 4](#) for reproductive criteria for male ([Section 10.4.1](#)) and female ([Section 10.4.2](#)) participants.

Disease Characteristics:

2. Previous diagnosis of CeD, based on documentation in the source data:
 - Positive celiac serology (eg, tissue transglutaminase IgA antibody and/or deamidated DGP IgG)

AND

 - Intestinal histology consistent with \geq Marsh Type 2 ([Section 10.11](#)) or with evidence of villous atrophy.
3. Have HLA-DQ2.5 genotype (HLA-DQA1*05 and HLA-DQB1*02 (homozygotes or heterozygotes)).
4. Negative or weak positive for transglutaminase IgA AND negative or weak positive for DGP-IgA/IgG during screening.
 - For tTG, a result of ≤ 10 U/mL will be considered negative or weak positive.
 - For DGP, a result of < 30 U/mL will be considered negative or weak positive.
5. **Part B ONLY (prior to randomization):** Demonstrates a symptomatic response following a 1-day oral GC performed during Run-in, defined as having at least 1 moderate to severe GI symptom (either diarrhea, abdominal pain, bloating, or nausea) the day of the GC.
 - Refer to [Section 8.2.1.1](#) for symptomatic response criteria.

Other Inclusion Criteria:

6. Have followed a gluten-free diet for ≥ 12 months immediately prior to study entry (self-reported).
7. Capable of understanding the ICD, complying with protocol requirements, and has signed the ICD.

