8.4.5.1. Exposure During Pregnancy

An EDP occurs if:

- A female participant is found to be pregnant while receiving or after discontinuing study intervention during the mandatory contraception period (see [Appendix 4](#)).
- A male participant who is receiving or has discontinued study intervention inseminates a female partner during the mandatory contraception period (see [Appendix 4](#)).
- A female nonparticipant is found to be pregnant while being exposed or having been exposed to study intervention because of environmental exposure. Below are examples of environmental EDP if they occur within 21 days after exposure:
- A female family member or healthcare provider reports that she is pregnant after having been exposed to the study intervention by ingestion, inhalation, or skin contact.
- A male family member or healthcare provider who has been exposed to the study intervention by ingestion, inhalation, or skin contact then inseminates his female partner prior to or around the time of conception.

The investigator must report EDP to Pfizer within 24 hours of the investigator's awareness, irrespective of whether an SAE has occurred. The initial information submitted should include the anticipated date of delivery (see below for information related to termination of pregnancy).

- If EDP occurs in a participant/participant's partner, the investigator must report this information to Pfizer on the CT SAE Report Form and an EDP Supplemental Form, regardless of whether an SAE has occurred. Details of the pregnancy will be collected after the start of study intervention and until 12 weeks after the last dose.
- If EDP occurs in the setting of environmental exposure, the investigator must report information to Pfizer using the CT SAE Report Form and EDP Supplemental Form. Since the exposure information does not pertain to the participant enrolled in the study, the information is not recorded on a CRF; however, a copy of the completed CT SAE Report Form is maintained in the investigator site file.

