10.4.4. Contraception Methods

Contraceptive use by men or women should be consistent with local availability/regulations regarding the use of contraceptive methods for those participating in clinical trials.

The following contraceptive methods are appropriate for this study:

Highly Effective Methods That Have Low User Dependency

1. Implantable progestogen-only hormone contraception associated with inhibition of ovulation.
2. Intrauterine device.
3. Intrauterine hormone-releasing system.
4. Bilateral tubal occlusion.
5. Vasectomized partner.
 - Vasectomized partner is a highly effective contraceptive method provided that the partner is the sole sexual partner of the WOCBP and the absence of sperm has been confirmed. If not, an additional highly effective method of contraception should be used. The spermatogenesis cycle is approximately 90 days.

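### Sections 10.4.1 and 10.4.2 are headed for Parts A and B only, so it is unclear whether they bind Part C; separately, Section 4.2.1 disagrees with them on barrier use and on sterile men

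*Protocol*

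**What the plan says.** **Where the conditions are.** Inclusion Criterion 1 (protocol Section 5.1) refers to Appendix 4 "for reproductive criteria for male" and for female participants, naming Sections 10.4.1 and 10.4.2. It carries no part limit. Section 5 requires all inclusion and exclusion criteria to be met before randomization in Part C.

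**How they are labelled.** The two sections are headed "10.4.1. Male Participant Reproductive Inclusion Criteria (Parts A and B" and "10.4.2. Female Participant Reproductive Inclusion Criteria (Parts A and B". The table of contents labels them the same way. Neither names Part C. Yet 10.4.2 opens with "The criteria below are part of Inclusion Criterion 1 (Age and Sex", which ties it to a criterion that covers all parts.

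**What they require.** Section 10.4.2 requires that a woman is neither pregnant nor breastfeeding, does not donate eggs for 21 days after the last dose, and meets one of three further conditions. She may be outside the childbearing-potential definition. She may use a highly effective method with low user dependency. Or she may use a highly effective user-dependent method, for which the text adds: "In addition to her use of the highly effective method above, she agrees to concurrently use an effective barrier method". Section 10.4.1 requires men to refrain from sperm donation and either to be abstinent or to use a condom.

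**What Section 4.2.1 says.** It states that "the use of a highly effective contraception and a barrier method is required for WOCBP", without distinguishing method types. It asks one reliable method of men who are not sterile, and gives a period of at least 21 days after the last dose. It also says that no embryo-fetal study has been done and that effects on conception, pregnancy and lactation are unknown.

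**The concern.** There are two faults, and neither causes the other.

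The first is scope. Part labels decide what applies elsewhere in this protocol: Inclusion Criterion 5 is marked as Part B only, and the heading of Section 4.3.2 names Part C where Part C is meant. A site screening for Part C could therefore reasonably take the label on 10.4.1 and 10.4.2 as a limit. Another site could follow the cross-reference from Criterion 1 and apply both sections.

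The second is a contradiction between Section 4.2.1 and Appendix 4 on what contraception a participant must use. It is present in all three parts.

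At stake are consistent eligibility decisions and participant protection for a product whose effects on pregnancy and lactation the protocol calls unknown. The statistical analysis is not at stake.

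**Working it through.** No formula applies to the main point, so the passages are set side by side.

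**Step 1: which conditions reach Part C by another route.**

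| Condition | In 10.4.1 or 10.4.2 | Elsewhere, applying to Part C |
|---|---|---|
| Not pregnant | 10.4.2 | Part C schedule: serum test at screening, negative test before dosing or gluten challenge. Section 7.1.2: same restriction. Section 8.3.6: second negative test before dosing, and exclusion if a serum test resolving an unclear urine result is positive |
| Contraception period | 10.4.1, 10.4.2 | Section 4.2.1: at least 21 days, no part limit |
| Not breastfeeding | 10.4.2 | No eligibility text. Section 8.4.5.2 makes it a reportable exposure only |
| No egg donation | 10.4.2 | None found |
| No sperm donation | 10.4.1 | None found |

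The 21 days in 4.2.1 stand at the end of a sentence that covers women first and then men; I read them as covering both. The Part C contraception checks fit that reading. They run to Day 28, and the last dose is on Day 7: 28 − 7 = 21 days.

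Breastfeeding, egg donation and sperm donation therefore depend, in Part C, on one cross-reference to sections whose headings omit Part C.

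**Step 2: the two readings for Part C.**

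- If Criterion 1 and Section 5 govern, 10.4.1 and 10.4.2 apply in full, and the conflict in Step 3 comes with them.
- If the headings govern, only 4.2.1 sets the contraception method in Part C, and the three conditions above have no eligibility text.

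**Step 3: Section 4.2.1 against Appendix 4, all parts.**

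| Participant | 4.2.1 | 10.4.1 or 10.4.2 |
|---|---|---|
| Woman of childbearing potential, intrauterine device, no barrier | Not met: barrier required | Met: low-user-dependency method suffices |
| Sterile man, not abstinent, no condom, no sperm donation | Outside the requirement | Not met: no exemption stated |

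The intrauterine device appears in 10.4.4 under "Highly Effective Methods That Have Low User Dependency", so the first row is a case the protocol itself provides for.

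**Step 4: size.** Planned enrolment in Section 9.5 is 6 to 12 in Part A, about 16 in Part B and about 104 in Part C. The totals are 6 + 16 + 104 = 126 and 12 + 16 + 104 = 132. Part C is 104/132 = 78.8% to 104/126 = 82.5%. This is the share enrolled in the part whose coverage is unclear. It includes men and women not of childbearing potential, and it does not measure the barrier conflict. The documents give no count of women of childbearing potential, contraceptive methods or breastfeeding women.

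**The case against.** The strongest reply is that the heading is a leftover label from before Part C was added, and that the operative text is clear. Criterion 1 has no part limit, part-limited criteria say so, Section 5 applies all criteria to Part C, and the body of 10.4.2 is not limited by part. This carries weight. It makes the fault an ambiguity rather than a missing criterion, and it is probably what the sponsor intended. It does not remove the ambiguity, because the headings still exclude Part C by their wording.

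A reader might go further and infer that Part C has no pregnancy or breastfeeding criterion, or that a breastfeeding woman meets every Part C criterion. The documents do not support either. Pregnancy is covered by the Part C schedule and Sections 7.1.2 and 8.3.6. The breastfeeding inference holds only if the heading overrides Criterion 1, Section 5 and the body of 10.4.2.

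A reader might also infer that exposure reporting lapses in Part C, because Section 8.4.5.1 relies on exposure "after discontinuing study intervention during the mandatory contraception period" and refers to Appendix 4. That reference has no part limit and 4.2.1 gives a period, so the effect is uncertainty and not loss.

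On the second fault, it can be said that 4.2.1 is a rationale section that defers to Appendix 4, and that eligibility is decided through 5.1. That is fair as to rank, but 4.2.1 states a requirement and the appendix it refers to does not agree. The point on men is weaker, because 10.4.1 is merely silent on sterility and a man can comply with both texts.

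Finally, 10.4.2 calls the list in 10.4.4 complete, yet the list as read shows only low-user-dependency methods. That cannot be treated as an established error. Sections 5.3.1, 6.9.2 and 10.4.3 presuppose other methods, so entries may have been lost when the text was extracted.

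**Conclusion.** The point holds in limited form. It is ambiguous whether 10.4.1 and 10.4.2 bind Part C, and this matters most for breastfeeding and for egg and sperm donation, which have no other eligibility text. Independently, 4.2.1 conflicts with 10.4.2 on when a barrier method is needed, and differs from 10.4.1 on sterile men, in all three parts.

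The scope question concerns the part holding 79% to 83% of planned participants. A reader might take that range as the share touched by the contraception conflict. It is not: the conflict is not specific to Part C, and its size is unknown. Sample size, power and alpha are unaffected.

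The conclusion assumes that the headings are as printed and that no other eligibility text on breastfeeding or gamete donation exists in the protocol. It does not depend on whether the list in 10.4.4 is complete. This is a fault of wording and consistency, worth correcting because the protocol itself calls the effects on pregnancy and lactation unknown.

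**What to change.** Reconcile Sections 4.2.1, 5.1, 10.4.1 and 10.4.2 into one consistent statement and make its scope for Part C explicit, including breastfeeding and egg and sperm donation. State the position on sterile men once. Check that the method list in 10.4.4 is complete and agrees with the reconciled rule. Which contraception rule applies is for the sponsor to decide; this review takes no side.

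The cost is a wording amendment and a letter to sites, with no new procedure or data. The Part C SAP (version history, 13 June 2025) records that the study was terminated. If Part C enrolment has ended, the useful action is to document which rule sites applied in Part C.
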